[figure not shown]

Official Title: Effect of supplementation with *Euterpe edulis* on the physical and mental performance of healthy men submitted to physical exercises

Ethical committee Protocol No: 6.202.888

Study protocol

1. Type of study

This is a clinical study, double blind, with the purpose of offering the juice of *E. edulis*, daily for 4 weeks before the day of the final evaluation, compared to the control. There will be about 40 men, aged 19 to 30 years, who perform regular physical exercises, in total of 150 min per week, at a minimum of 3 months.

2. Experimental Protocol

The men will be randomized into two groups, called GJ who will receive the sample and GP who will receive the placebo. The sample consists of 250 mL of juçara juice and the placebo which is 250 mL of water with pectin and natural dye. Research subjects will maintain their exercise routine, as well as fill out a food diary that will be sent electronically. The research will be for 11 days, and on day 1 (D1) of the research he will have the blood collected. On day 11 of the D11 survey, at time zero he will have the blood collected, and then consume the sample or the placebo. Two hours after he will be subjected to the battery of exercises, following 1. Dorsal dynamometer, 2. shoulder dynamometer, 3. manual dynamometer, 4. ergospirometry + electrocardiogram + digital lactate, 5. jump test for 1 min (amounts of jumps), 6. Pollock abdominal test and 7. functional mobility test. At the end, the blood will be collected, and a psychological form will be applied. After 2 and 7 days of physical exercise will be applied visual pain test.

3. The size of the sample

The calculation of the sample of patients for this study was performed using the software G*Power3.1.9.7 (Public domain). Considering the alpha value equal to 0.05 and the power of test $1 - \beta$ as 95% (0.95, that is, determining that the probability of type II error (β) should not be greater than 5%), the value of 20 patients was reached.

The selection will be simple random probabilistic from a total population of patients who fit the inclusion criteria. Among the inclusion criteria are: being male, aged between 19 and 30 years and practicing physical exercises regularly for at least 3 months. Among the exclusion criteria are people who have motor problems, cardiovascular changes, have type I and II diabetes, smokers, athletes, cognitive deficits, and psychomotor disorders. Each patient will be evaluated at the beginning of the exercise and at the end of the exercise. Patients were randomly divided into 2 groups: treatment with placebo product and with the supplement of *E. edulis*.

4. Ethical issues

The study will be conducted after approval by the Ethics Committee on Research with Human Beings of the Vila Velha University and conducted in accordance with the Declaration of Helsinki. The clinical study will also be registered with REBEC, and will only be initiated after all ethical approvals. All participants will sign a written agreement (ICF).

As for the risks, in a previous study with 39 participants, none presented pictures of allergy or gastric or intestinal intolerance to JFJ and as a benefit, such a study demonstrated a positive effect on the acute adaptive inflammatory response (MENDES et al., 2021).

5. Inclusion criteria

Among the inclusion criteria are:

- Being male
- Aged between 19 and 30 years old
- Practicing physical exercises regularly for at least 3 months

6. Exclusion Criteria

Men who use:

- Steroids
- Anabolics
- Taurine
- BCCA
- Exogenous supplementation

7. Removal criteria

Among the exclusion criteria are people who have:

- Motor problems
- Cardiovascular changes
- Have type i and ii diabetes
- Smokers
- Athletes
- Cognitive deficits
- Psychomotor disorders.

Each patient will be evaluated at the beginning of the exercise and at the end of the exercise. Patients will be randomly divided into 2 groups: treatment with a placebo product and with an E. edulis supplement.

8. Intervention

On day 11 of the D11 survey, at time zero he will have the blood collected, and then consume the sample or the placebo. Two hours after he will be subjected to the battery of exercises, following 1. Dorsal dynamometer, 2. shoulder dynamometer, 3. manual dynamometer, 4. ergospirometry + electrocardiogram + digital lactate, 5. jump test for 1 min (amounts of jumps), 6. Pollock abdominal test and 7. functional mobility test. At the end, the blood will be collected, and a psychological form will be applied. After 2 and 7 days of physical exercise will be applied visual pain test.

9. Preparation of Juçara juice

The preparation will be obtained with the same methods already well established in previous studies (SCHULZ et al., 2016.; MENDES et al., 2021). Participants will receive 250 ml of water + purple dye + pectin (control) or commercial samples of juçara (*E.edulis*) refrigerated to 4°C to 10°C, per day, for 10 days, and on the 11th will be the exercise and on this day will be administered the juice of the juçara 2 h before on the day of the monitored exercise. The chemical characterization of *Euterpe edulis* will be with at least 350.0 + or - 17.5 mg of total phenolics (gallic acid equivalent), 186.0 + or - 7.5 mg of total monomeric anthocyanins (cyanidin 3-glycoside), 0.73 + or less 0.01 g of proteins, and 2.75 + or - 0.03 g of lipids (ether extract). During the 10 days of previous treatment, maintain the routine of physical exercises.

10. Values evaluated

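### Section 1 sets 4 weeks of daily juice before the final evaluation, but sections 2 and 9 describe an 11-day study with 10 days of intake before the test day

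*Combined protocol and SAP*

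**What the plan says.** **Duration.** Section 1 (Type of study), which states the purpose of the trial, has the juice taken "daily for 4 weeks before the day of the final evaluation". Section 2 (Experimental Protocol) says "The research will be for 11 days", with the first blood sample on day 1 and the exercise battery on day 11. Section 9 (Preparation of Juçara juice) supplies juice or control "per day, for 10 days, and on the 11th will be the exercise", adds a serving on day 11 two hours before exercise, and then repeats the shorter period: "During the 10 days of previous treatment, maintain the routine of physical exercises".

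**Draw and drink on the evaluation day.** For day 11, section 2 says that "at time zero he will have the blood collected, and then consume the sample or the placebo". Section 8 (Intervention) repeats this and continues "Two hours after he will be subjected to the battery of exercises". Section 10.3 (blood samples and biomarkers) names no study day. It takes a resting sample 1 hour before exercise and has the men drink juice or placebo from that point on.

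**Blood samples.** Section 2 lists a day 1 sample ("on day 1 (D1) of the research he will have the blood collected"), one at time zero on day 11, and one after the battery ("At the end, the blood will be collected"). Section 8 has the two day 11 samples and does not mention day 1. Section 10.3 lists samples 1 hour before exercise, 3 minutes after it, and after 24 hours of rest. Section 11 plans a repeated-measures ANOVA without naming time points.

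**The concern.** The length of supplementation is part of the treatment being compared with placebo. With two incompatible lengths in the current text, the plan does not say what exposure the trial tests. The longer figure stands in the statement of purpose and the shorter one in the operational sections. A report that takes its aim from section 1 and its conduct from sections 2 and 9 could therefore attach a 4-week claim to about 10 days of intake, or the reverse.

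Two smaller matters follow. The interval between the evaluation-day drink and exercise may also depend on which section is followed. And because section 11 names no time points, the list of blood samples decides which ones enter the repeated-measures analysis. In section 2 the day 1 draw is the only listed sample that could precede the intake period, and the 24 h sample appears only in section 10.3.

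**Working it through.** **1. Servings before the evaluation day**, at one serving a day.

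- Section 1: 4 weeks × 7 days = 28.
- Section 9, consistent with days 1 to 10 of section 2: 10.
- Difference: 28 − 10 = 18 servings. Ratio: 28 / 10 = 2.8.

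The counting convention does not remove the gap. If a test-day serving is added on both sides, the counts are 29 and 11, and the difference is still 18.

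**2. Can both periods hold?** Only if a further 18 days of intake came before day 1. The protocol describes no run-in, extension or second phase, and section 9 gives the treatment preceding the exercise day as 10 days. No amendment log or redaction bears on these sentences.

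**3. Timing on the evaluation day, if section 10.3 describes day 11.** Put the start of exercise at 0 h.

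| Section | Pre-exercise draw | Drink |
|---|---|---|
| 2 and 8 | before the drink, so at −2 h or earlier | −2 h |
| 9 | not stated | −2 h |
| 10.3 | −1 h | after the draw, so at −1 h or later |

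A draw that precedes a drink taken at −2 h cannot also be at −1 h. On this reading the drink-to-exercise interval is 2 h in sections 2, 8 and 9 and at most 1 h in section 10.3. The 1 h bound also assumes that drinking follows the draw on the day of exercise, since section 10.3 gives no clock time for the drink.

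**4. Blood samples.**

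- Section 2: day 1; day 11 before exercise; day 11 after exercise.
- Section 8: day 11 before exercise; day 11 after exercise.
- Section 10.3: before exercise; 3 minutes after; after 24 hours of rest.

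Day 1 appears only in section 2 and the 24 h sample only in section 10.3. Neither section excludes the other's sample. A draw at the end of the battery and a draw 3 minutes after exercise can be the same draw.

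**The case against.** On duration, the best defence is that 4 weeks occurs once, in a summary sentence, while sections 2, 8 and 9 all work to day 11. A reader might infer that the 11-day schedule is the true one and that section 1 holds a leftover phrase. The documents do not support choosing either: no section is given precedence, and section 1 is where the purpose is stated. The agreement among the later sections stands as a fact, but it does not resolve the conflict. It is also fair to say that misreported exposure is a risk and not something the documents show to have happened.

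On timing, the objection has more force. Section 10.3 names no day and speaks of intense strength exercise, whereas the day 11 battery also includes ergospirometry, a jump test and a mobility test. Its wording on randomisation and drinking reads like a single-session design, which fits poorly with men who have already had 10 days of intake. Against that, day 11 is the only monitored exercise session the protocol describes. The timing conflict should therefore be stated as conditional.

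On samples, a reader might infer that the lists in sections 2 and 10.3 contradict each other. They need not: day 1, pre-exercise, post-exercise and 24 h samples could all be taken. Nor do pain tests 2 and 7 days after exercise contradict the stated 11 days in any serious way, since section 2 announces them in the same paragraph.

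**Conclusion.** The duration conflict is established. Section 1 implies 28 servings before the evaluation day and section 9 implies 10, and the documents do not say which governs. This rests only on one serving a day and on the text as it stands. It must be corrected, and that rating depends on duration alone.

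The draw and drink timing conflict holds with moderate confidence, on condition that section 10.3 describes the day 11 session and that its drink follows the draw on that day.

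The sample lists are incomplete rather than contradictory, and need only clarification.

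Nothing here shows which period or timing was intended, or that any participant received something other than what was planned.

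**What to change.** - Reconcile sections 1, 2, 8 and 9 to one supplementation period, chosen and stated by the investigators, and align the aim, the visit labels and the conclusion wording with it.
- State which session section 10.3 describes. If it is day 11, reconcile its draw and drink timing with sections 2, 8 and 9.
- Give a single list of blood samples, saying whether the day 1 and 24 h samples are both taken, and name the resulting time points in the section 11 repeated-measures ANOVA.
- If participants have already been treated, document the schedule actually followed and report that exposure.

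**Cost.** If nobody has been treated and the day 1 to day 11 schedule is the intended one, this is a text amendment only. If the intended period differs, visit dates, the food-diary period and product supply change as well. If treatment has begun, the work is to document the schedule followed and match the report to it.

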10.6 Subjective analysis of fatigue

A questionnaire will be developed about the subjective perception of patients about the effects of the treatment employed in the recovery of muscle fatigue. The questions will be based on the Chalder scale and the International Short-Form Physical Activity Questionnaire (IPAQ-SF) (LEE et al., 2011). However, the feeling of improvement or not of physical fatigue after exercise will be the focus of the preparation of a new and unprecedented questionnaire

11. Statistical analysis

The results will be expressed as mean \pm SEM (standard error of the mean). Statistical analysis will be performed by one-way analysis of variance (ANOVA) (repeated measures), followed by Tukey's post hoc test, using the Prism software (Prism 6.0, GraphPad Software, Inc., San Diego, CA, USA). The differences will be considered significant when $p < 0.05$.

REFERENCES

ARCURI, J. F. et al. Validity and Reliability of the 6-Minute Step Test in Healthy Individuals: A Cross-sectional Study. **Clinical Journal of Sport Medicine**, v. 26, n. 1, p. 69-75, Jan. 2016.

BUTCHER, J. T. et al. Effect of myostatin deletion on cardiac and microvascular function. **Physiological Reports**, v. 5, n. 23, e13525, Dec. 2017.

CABARKAPA, D. et al. Position-specific differences in countermovement vertical jump force-time metrics in professional male basketball players. **Front Sports Act Living**, v. 20, n. 5, p. 1218234, Jul. 2023.

CARDOSO, A.L. et al. An Update on the Biological Activities of *Euterpe edulis* (Juçara). **Planta Médica**, v. 84, n. 8, p. 487-499, may., 2018.

CARROLL, T. J.; TAYLOR, J. L.; GANDEVIA, S. C. Recovery of central and peripheral neuromuscular fatigue after exercise. **Journal of Applied Physiology**, v. 122, n. 5, p. 1068-1076, May. 2017.

ELY, M. R. et al. A single dose of histamine-receptor antagonists before downhill running alters markers of muscle damage and delayed-onset muscle soreness. **Journal of Applied Physiology** v. 122, n. 3, p. 631-641, mar. 2017.

FANG, P. et al. Adipose-Muscle crosstalk in age-related metabolic disorders: The emerging roles of adipo-myokines. **Ageing Research Reviews**, v. 84, p. 101829, Feb. 2023.

FELZENSZWALB, I. et al. Toxicological evaluation of *Euterpe edulis*: a potential superfruit to be considered. **Food and Chemical Toxicology**, v. 58, p. 536-44, Aug. 2013.

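### The placebo is described only as water, pectin and dye, with no taste match and no blinding procedure, so the double-blind label is not secured for the effort-dependent and self-rated outcomes

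*Combined protocol and SAP*

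**What the plan says.** Section 1 gives the blinding claim and a duration: "This is a clinical study, double blind, with the purpose of offering the juice of *E. edulis*, daily for 4 weeks". It does not say who is blinded or by what means.

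The control is described twice. Section 2 has: "The sample consists of 250 mL of juçara juice and the placebo which is 250 mL of water with pectin and natural dye". Section 9 has: "Participants will receive 250 ml of water + purple dye + pectin (control) or commercial samples of juçara". The only named control ingredients are water, pectin and a dye, called natural in one place and purple in the other.

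Section 9 also specifies the juice: "at least 350.0 + or - 17.5 mg of total phenolics (gallic acid equivalent", "186.0 + or - 7.5 mg of total monomeric anthocyanins (cyanidin 3-glycoside" and "0.73 + or less 0.01 g of proteins, and 2.75 + or - 0.03 g of lipids (ether extract". Carbohydrate and total energy are given for neither drink.

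The outcomes include three dynamometer tests, ergospirometry, a one-minute jump count, an abdominal test and a functional mobility test (sections 2 and 8), a step test and a plank test (10.4.3 and 10.4.4), and a visual pain test 2 and 7 days after exercise. Section 10.6 adds a new instrument: "A questionnaire will be developed about the subjective perception of patients about the effects of the treatment employed in the recovery of muscle fatigue". No primary outcome is named.

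**The concern.** A dye and pectin can imitate colour and thickness. Nothing listed would imitate the taste of a fruit juice. Each man drinks his product repeatedly before he is tested, so a drink that does not taste like juice has many chances to give itself away. If men form a correct belief about their arm, those on juice may try harder or rate their recovery better, and those on placebo the reverse. The comparison would then credit the juice with an effect of expectation, and no later analysis can reliably remove it.

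The outcome set makes this matter more than usual. Strength, jump and endurance scores depend on willingness to push, and operators who know the allocation could influence that. Pain is self-rated after all the servings described in sections 2 and 9 have been taken. The fatigue questionnaire asks directly about the perceived effect of treatment. With no primary outcome named, the less exposed blood markers have no priority over these measures.

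**Working it through.** **Plan's own figure.** The only computed figure is the 20 patients in section 3 (alpha 0.05, power 95%). It cannot be reproduced, because no effect size, SD, test or sidedness is given and the text does not say whether 20 is a total or per arm. Working backwards with a two-sided two-sample t-test, 95% power needs a difference of 1.17 SD at 20 per arm or 1.71 SD at 10 per arm. The blinding point does not depend on this figure, but the ambiguity is why both sizes are shown below.

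**Step 1: what is matched.**

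| Feature | Juice (sections 2, 9) | Control (sections 2, 9) |
|---|---|---|
| Volume | 250 mL | 250 mL |
| Colour | juice | dye, not identified |
| Texture | juice | pectin |
| Flavour, acid, sweetener | juice | none listed |
| Lipid, protein | 2.75 g, 0.73 g | none listed |
| Carbohydrate | not stated | not stated |
| Container, coding, dispensing | not described | not described |

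Even the match in look and texture is inferred from the ingredients; the document does not claim or test it.

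**Step 2: how often the drink is tasted.** Sections 2 and 9 imply 10 daily servings plus one on D11: 10 + 1 = 11. Section 1 says 4 weeks, which would be 4 × 7 = 28 daily servings. Exposure is repeated on either reading.

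**Step 3: illustration of the consequence.** Assumptions, none from the document: the juice has no true effect; expectation shifts the arm difference by b SD; allocation is 1:1; the test is a two-sided two-sample t-test at 0.05. With n per arm, df = 2n − 2, noncentrality λ = b√(n/2), and

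P(reject) = P(T > t_crit) + P(T < −t_crit), where T is noncentral t with df and λ.

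- n = 20 (about 40 men, section 1): df = 38, t_crit = 2.024, √(20/2) = 3.162.
- n = 10 (if 20 is the total): df = 18, t_crit = 2.101, √(10/2) = 2.236.

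| b (SD) | λ, n = 20 | P(p<0.05), n = 20 | λ, n = 10 | P(p<0.05), n = 10 |
|---|---|---|---|---|
| 0 | 0 | 5.0% | 0 | 5.0% |
| 0.2 | 0.632 | 9.5% | 0.447 | 7.1% |
| 0.3 | 0.949 | 15.2% | 0.671 | 9.7% |
| 0.5 | 1.581 | 33.8% | 1.118 | 18.5% |

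Unblinding need not be complete. If half the men guess correctly and that produces 0.5 SD among them, the net shift is 0.5 × 0.5 = 0.25 SD, which gives 12.0% at 20 per arm and 8.3% at 10 per arm.

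**Step 4: documented nutrient gap.** At assumed factors of 9 kcal/g for fat and 4 kcal/g for protein: 2.75 × 9 + 0.73 × 4 = 24.75 + 2.92 = 27.7 kcal per serving. Any carbohydrate difference is additional and unknown.

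**Step 5: timing.** Sections 2, 8 and 9 place the D11 drink 2 hours before the exercise. Section 10.3 has blood drawn 1 hour before exercise and the drink taken from that moment. These statements conflict, as do the 4 weeks and the 10 days plus D11.

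**The case against.** The strongest reply is that absence of description is not absence of matching. Section 9 opens by referring to methods established in earlier studies, and a fuller placebo recipe might be found there. This does not settle the matter: the same section goes on to state the control's composition outright and reports no sensory match.

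Second, this is a parallel-group trial, so no man tastes both drinks. Recognising a placebo requires some idea of how juçara juice should taste, or at least of how juice should taste. That stands. A reader might infer that the blind will fail; the documents do not show it, and the supportable statement is that the blind is not secured.

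Third, a reader might infer that the lipid and protein gap confounds the comparison and that the placebo must be matched on energy. The documents do not support that. The title and section 1 set out to test supplementation with the juice, and its nutrients are part of it; section 10.5 even assays its amino acids and total protein. Energy matching would ask a different question, and the documented gap of 27.7 kcal is small.

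Fourth, a reader might suspect that a natural purple dye contains anthocyanins and pulls the arms together. The dye is not identified, natural and purple are compatible descriptions, and no bias can be claimed from them.

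Finally, the shifts of 0.2 to 0.5 SD have no source in the plan, and a t-test stands in for the repeated-measures ANOVA of section 11. Both criticisms are correct, so the percentages show sensitivity and are not estimates for this trial.

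**Conclusion.** The point holds in a limited form. As written, the plan gives a control that imitates at most colour and texture, and names no procedure to keep participants or operators blind. The double-blind label is therefore unsupported for the effort-dependent tests, the pain test and the fatigue questionnaire. It matters less for blood markers, which expectation is less likely to move.

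If expectation did shift an outcome by 0.2 to 0.5 SD with an inactive juice, the nominal 5% error rate would become 9.5% to 33.8% at 20 per arm, or 7.1% to 18.5% at 10 per arm. These figures rest on the assumed shifts, 1:1 allocation and a simple two-arm t-test. The nutrient gap is a note for interpretation, not a flaw in the control. This is a cheap improvement, and it must be made before the first serving because lost blinding cannot be restored afterwards.

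**What to change.** 1. In sections 2 and 9, add food-grade flavour, acid and sweetener so that the placebo resembles the juice in taste as well as colour and texture, and name the dye.
2. Supply both drinks in identical, coded, opaque containers, and state in section 1 that participants and test operators are blinded.
3. Add a one-item treatment guess, answered by each man before the D11 exercise battery so that his performance does not shape the answer. Report it descriptively by arm beside the effort-dependent and self-rated outcomes. The question draws some attention to allocation just before testing, so word it identically in both arms.
4. If taste cannot be matched, describe the trial as matched for appearance only, and treat those outcomes as open to expectation bias.
5. Report the full composition of both drinks, including carbohydrate.
6. Reconcile the statements on duration (section 1 against sections 2 and 9) and on the timing of the drink before exercise (sections 2, 8 and 9 against section 10.3).

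Cost: one placebo batch to reformulate, coded containers, one extra question and a few lines of text. No change to sample size or schedule of assessments is needed.

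### Does the 20 in the sample-size section contradict the planned 40 men and make the 95% power claim wrong?

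*Combined protocol and SAP*

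**What the plan says.** Section 1 (Type of study) fixes the planned size: "There will be about 40 men, aged 19 to 30 years, who perform regular physical exercises". Section 2 (Experimental Protocol) describes two parallel arms: "The men will be randomized into two groups, called GJ who will receive the sample and GP who will receive the placebo". No allocation ratio is given.

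Section 3 (The size of the sample) says that the calculation was "performed using the software G*Power3.1.9.7 (Public domain"). It starts from "Considering the alpha value equal to 0.05 and the power of test" of 95% and ends with "the value of 20 patients was reached". It does not say whether 20 is a total or a group size. It gives no outcome, effect size, SD, test, sidedness, correlation or dropout.

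Section 11 (Statistical analysis) adds: "Statistical analysis will be performed by one-way analysis of variance (ANOVA) (repeated measures"), with Tukey's test afterwards and a 0.05 threshold. It names no juice-versus-placebo contrast.

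**The concern.** Three things look wrong together.

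- A calculation that ends in 20 sits next to a planned enrolment of 40, and no sentence connects them.
- A power of 95% means nothing without an effect size, and the effect needed for a simple two-group comparison of this size is large.
- If the software run mirrored the one-way repeated-measures model of Section 11, then 20 men might give power for a change over time. Exercise alone can produce such a change, whatever the effect of the juice.

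If all this held, readers would credit the trial with a 5% risk of missing a real effect when the risk was far higher. A null result would then be over-read, and it would be unclear when enrolment is complete.

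**Working it through.** **Inputs from the documents.** Alpha 0.05, power 0.95 and 20 patients (Section 3); about 40 men (Section 1); two groups (Section 2).

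**Assumptions, because the documents are silent.** 1:1 allocation, two-sided testing, and the effect sizes and correlations named below.

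**Step 1: reproduce the 20.** This cannot be done, because no effect size or test is stated. One can only ask which effects are compatible with it.

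**Step 2: simple comparison at one time point.** With n per group, the two-sample t-test has 2n − 2 degrees of freedom and noncentrality d·√(n/2), where d is the difference in SD units. Solving for d:

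| Men in total (per group) | d for 80% power | d for 95% power | Power at d = 0.5 | Power at d = 0.8 | Power at d = 1.0 |
|---|---|---|---|---|---|
| 20 (10) | 1.33 | 1.71 | 18.5% | 39.5% | 56.2% |
| 40 (20) | 0.91 | 1.17 | 33.8% | 69.3% | 86.9% |

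For 95% power at d = 0.8, 42 per group (84 men) would be needed.

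**Step 3: outcomes measured more than once.** For a difference in change between two occasions with within-person correlation r, the threshold in raw SD units is the Step 2 value times √(2(1 − r)). With 40 men and r = 0.7 this is 1.17 × √0.6 = 0.91.

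| Men in total | r = 0.5 | r = 0.7 | r = 0.8 | r = 0.9 |
|---|---|---|---|---|
| 20 | 1.71 | 1.32 | 1.08 | 0.76 |
| 40 | 1.17 | 0.91 | 0.74 | 0.52 |

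Baseline-adjusted ANCOVA at r = 0.7 gives 1.22 SD (20 men) and 0.84 SD (40 men). The range of 1.2 to 1.7 SD therefore belongs to one choice of test, not to the design as a whole.

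**Step 4: can about 20 come from a calculation aimed at juice versus placebo?** For the group-by-time interaction with N men in total, m measurements and correlation ρ, the noncentrality is λ = f²·N·m/(1 − ρ). The degrees of freedom are m − 1 and (N − 2)(m − 1).

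- f = 0.40, m = 3, ρ = 0.5, N = 20: λ = 0.16 × 20 × 3/0.5 = 19.2, df 2 and 36, power 97.2%. N = 18 already gives 95.3%.
- f = 0.25, m = 4, ρ = 0.7, N = 20: λ = 0.0625 × 20 × 4/0.3 = 16.7, df 3 and 54, power 92.6%. With equal groups, N = 24 is the first total to reach 95%.

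Three measurements fit the blood draws in Section 2 (D1, and before and after exercise on D11). The 24-hour sample in Section 10.3 would make four.

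For a pure time effect with m = 3 and ρ = 0.5, N = 20 corresponds to f = 0.373. For the interaction it corresponds to f = 0.374. A result of 20 therefore cannot reveal which option was used.

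**Step 5: 20 against 40.** Two groups of 20 make 40. If 20 was instead a required total, 40 exceeds it. Section 3 reports the result of a calculation and nowhere says that enrolment ends at 20.

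**The case for a change.** The best counter-argument concerns the performance tests. Sections 2 and 8 schedule dynamometry, ergospirometry and the jump, abdominal and mobility tests once, on D11, and the only measurement they list for D1 is a blood draw. Without a baseline no correlation can help, so 1.17 SD with 40 men is the right yardstick for these outcomes.

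The software inputs in Step 4 are not modest either. With three occasions, f = 0.40 requires group deviations ±g with mean g² = 0.16. The pattern with the smallest spread is (a, a, −2a), so 2a² = 0.16 and a = 0.283. The juice–placebo gap then shifts by 2 × 3a = 1.70 SD between two occasions. For f = 0.25 with four occasions the corresponding minimum is 1.0 SD.

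Both points stand. At d = 0.8, an unadjusted comparison of 40 men misses the effect about 31% of the time (100 − 69.3), so the 95% should not be quoted as if it covered every outcome. It also stands that Section 3 cannot be reproduced as written and that its 20 lacks a label.

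These points show that the trial is small and its power statement incomplete. They do not show that the two numbers conflict or that the calculation was wrong for the effect its authors had in mind, which the documents do not disclose.

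**Conclusion.** No change to the plan follows. The figures of 1.71 SD (10 per group) and 1.17 SD (20 per group) are correct for an unadjusted, two-sided, 1:1 comparison at one time point. The documents neither name that test for Section 3 nor give an effect size against which 95% could be called false. The statement is unverifiable rather than shown to be in error. The 20 and the 40 agree if 20 is a group size, and the idea that 20 gives power only for a time effect is a guess about an unstated software setting.

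What remains is a reporting gap. Following the protocol means enrolling about 40 men. Labelling the 20, or writing in a detectable difference solved backwards from 40, would leave the enrolment, data, tests and results as they are. It would also not recover the effect on which the calculation was based. Anyone interpreting a null result can rely on the confidence interval for the juice–placebo difference, which does not depend on the planning power. This conclusion rests on Section 1 being the enrolment target, as it is the only place where the protocol says how many men will take part.

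### The day-11 performance tests have no described pre-treatment value, and the analysis adjusts for nothing, although weekly exercise volume has to be asked at screening and could serve as a covariate

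*Combined protocol and SAP*

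**What the plan says.** - **Population.** Section 1: "There will be about 40 men, aged 19 to 30 years, who perform regular physical exercises, in total of 150 min per week". The inclusion lists in Sections 3 and 5 ask only for regular exercise for at least 3 months and do not repeat the weekly minutes. Athletes are excluded; no upper limit in minutes is given.
- **Selection.** Section 3: "The selection will be simple random probabilistic from a total population of patients who fit the inclusion criteria". This is about drawing men from the eligible population.
- **Allocation.** Section 7: "Patients will be randomly divided into 2 groups: treatment with a placebo product and with an E. edulis supplement". Sections 2 and 3 say the same in other words. No stratification factor is named.
- **Timing.** Sections 2 and 8 place the exercise battery on day 11, two hours after the drink, and a visual pain test 2 and 7 days after the exercise. No performance or pain test before treatment is described. Blood is drawn on day 1 and again on day 11 before and after the battery. Section 10.3 adds a sample after 24 hours of rest.
- **Analysis.** Section 11 names a one-way repeated-measures ANOVA followed by Tukey's test at p < 0.05. It contains no covariate, no baseline term and no group term.

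**The concern.** Strength, aerobic capacity, jump count and abdominal endurance plausibly depend on how much a man trains. When an outcome is measured once, after treatment, all of that variation between men stays in the residual of the juice-placebo comparison. A pre-treatment test would remove part of it, but none is described. The next best variable is weekly exercise volume, which Section 1 makes necessary to ask and Section 11 leaves out.

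What is at stake is the width of the confidence interval, and hence the power, in a trial of about 40 men. The analysis as named also has nowhere to put the adjustment: a one-way repeated-measures ANOVA compares occasions within the same men, whereas juice and placebo are given to different men.

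**Working it through.** **1. The plan's own figure.** Section 3 gives alpha 0.05, power 95% and the result "the value of 20 patients was reached". It cannot be recomputed, because the effect size, SD, endpoint and test are not stated. Solving backwards with a two-sided two-sample t test (noncentral t), 95% power implies a standardised difference of 1.17 if 20 means per arm, and 1.71 if it means 20 in total. Twenty per arm matches the roughly 40 men of Section 1 and is used below.

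**2. Inputs.**
- From the documents: about 40 men, two arms, alpha 0.05.
- Assumed: equal arms (n = 20 each), two-sided testing, and the within-arm correlation r between weekly minutes and the outcome. The documents give no value for r, so 0.1 is shown as a low case and 0.3 to 0.6 as a working range.

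**3. Without adjustment.** Degrees of freedom are 2 × 20 − 2 = 38, and the noncentrality is d × √(n/2) = d × √10. Power of 80% requires d = 0.909, since 0.909 × 3.162 = 2.875.

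**4. With one covariate.** Residual variance is multiplied by 1 − r², the noncentrality becomes d × √10 / √(1 − r²), and the degrees of freedom fall to 37.

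| r | variance removed (r²) | noncentrality at d = 0.909 | power at d = 0.909 | d detectable at 80% power | unadjusted total equal to 40 adjusted, 40/(1 − r²) |
|---|---|---|---|---|---|
| none | 0% | 2.875 | 80.0% | 0.909 | 40 |
| 0.1 | 1% | 2.889 | 80.3% | 0.905 | 40.4 |
| 0.3 | 9% | 3.014 | 83.5% | 0.868 | 44.0 |
| 0.5 | 25% | 3.320 | 89.8% | 0.788 | 53.3 |
| 0.6 | 36% | 3.594 | 93.8% | 0.728 | 62.5 |

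The lost degree of freedom costs almost nothing: with r = 0 and the covariate in the model, power is 79.9%. The table takes the covariate as balanced between arms. Chance imbalance in it widens the adjusted interval slightly, so the figures are a little favourable, and at r = 0.1 the gain could vanish.

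**5. Which outcomes.** The table applies to outcomes measured only after treatment: the day-11 battery and the pain scores. Blood markers have a day-1 value, which is the more direct covariate for them.

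**The case against.** **The gain rests on an assumed correlation.** This stands. The weekly 150 minutes in Section 1 can be read as a common volume rather than a minimum, and excluding athletes narrows the range further. Both would pull r down, and at r = 0.3 the gain is only 80% to 83.5%.

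**Weekly minutes are a proxy.** This also stands. A pre-treatment performance test would be the more direct covariate. Section 3 does speak of evaluating each man at the beginning and end of the exercise, but that reads as the exercise session, not as a test before supplementation.

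**Repeated measures already remove stable differences between men.** True in part for blood markers, through within-man change. It does not help tests done on one occasion.

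A reader might also infer more than the documents support:
- *That the arms will be biased.* Chance imbalance in training causes no bias on average and does not inflate the type I error; the ordinary standard error already contains it.
- *That allocation is by coin toss and the arms will be badly unequal.* Simple randomness is stated for selection; the allocation method is not stated. Even a 24:16 split would raise the detectable difference only from 0.909 to 0.928 SD.
- *That the trial must stratify by training.* The documents offer no cut-point, and with covariate adjustment stratifying about 40 men adds little. It is a trade-off, not a necessity.
- *That staff could foresee assignments.* Nothing in the documents shows a mechanism. Ratio, list and concealment are not described, which is a reporting point only.

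**Conclusion.** The concern holds as a correctable loss of precision. For the day-11 performance tests and the later pain scores, the plan describes no pre-treatment value and adjusts for nothing, while a usable covariate has to be asked at screening under Section 1. With 20 men per arm and an assumed r of 0.3 to 0.6, leaving it out means a detectable difference of 0.91 SD instead of about 0.87 to 0.73 SD, or 80% power instead of about 84 to 94%. At r = 0.1 nothing material is lost. The size therefore depends on a correlation that the documents do not supply. The absence of the adjustment, and of a between-group model that could hold it, can be read directly from Section 11.

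**What to change.** 1. Record weekly exercise minutes as a number at screening, before allocation, and carry the Section 1 volume into the inclusion lists of Sections 3 and 5 so that it is always asked.
2. In Section 11, state a between-group model: ANCOVA with group and weekly minutes for outcomes measured once on day 11, and a mixed model with group, time, their interaction and weekly minutes for the pain scores. Report the adjusted juice-placebo difference with its confidence interval.
3. For blood markers, use the same type of model with the day-1 value as covariate instead of weekly minutes, and state that the day-1 sample is drawn before the first drink.
4. If a performance test before treatment is in fact done or is feasible, describe it and use its value as the covariate in place of weekly minutes.
5. As a reporting matter, add the allocation ratio, how the list is generated and how it is concealed.

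The cost of items 1 to 3 is one recorded number, one degree of freedom per model and a few lines of text. Item 4 would add a testing visit if the test is not already done.
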